#### **Trial Schema ARMS ARM B: Four Expansion Cohorts** ARM A: Single Agent Safety Lead-In & Cycle 1 **B1.** Measurable NBL **DOSE LEVEL 1 B2. Evaluable NBL 0-1 DLTs** 30 mg/kg magrolimab RP2D magrolimab **B3.** Measurable + 17.5mg/m^2 $+ 17.5 \text{mg/m}^2$ Osteosarcoma dinutuximab with **B4.** Osteosarcoma dinutuximab safety lead-in w/resectable (6 patients) pulmonary only relapse DOSE LEVEL -1 0-1 ≥ 2 **DLTs DLTs STOP TRIAL** ≥ 2 DLTs

[figure not shown]

Figure 2: Trial Schedule Schema

If ≥2 DLTs at Dose Level 1 (after week 3 or week 6), then reduce to DL-1 (20 mg/kg) and assess for safety, If ≥ 2 DLTs at DL-1, then STOP study

A. After cycle 2, Hu5F9-G4 (magrolimab) will be administered on Day 1 of the 1st and 3rd week of every subsequent cycle. Cycles may be repeated in the absence of disease progression or toxicity to a maximum of 12 cycles.

A. After cycle 2, Hu5F9-G4 (magrolimab) will be administered on Day 1 of the 1st and 3rd week of every subsequent cycle. Cycles may be repeated in the absence of disease progression or toxicity to a maximum of 12 cycles.

B1: Measurable NB B2: evaluable NB

B3: measurable OS

B4: OS with resectable pulmonary only relapse

pulmonary metastasectomy after at least 1 cycle and will require delay in starting subsequent cycle (for a maximum of 5 cycles post resection)

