### 6.2.1.2 Expansion Cohorts (Arm B) Regimen

Once the RP2D is determined from the dose finding cohort, 4 expansion cohorts will be enrolled on Arm B on this study as defined in **Section 6.4**. Expansion cohorts B1-B3 will receive a priming dose of Hu5F9-G4 (magrolimab) (1 mg/kg) on week 1, followed in week 2 with Hu5F9-G4 (magrolimab) administered at RP2D on Day 1 and dinutuximab 17.5 mg/m^2 on Days 2-5. Hu5F9-G4 (magrolimab) will be administered at RP2D on Day 1 of week 3 and 4. A maximum of 12 cycles (see Table 6) can be completed in the absence of DLT or disease progression.

Patients in Arm B Cohort B4 will be enrolled in two subgroups:

- 1. Those who are scheduled for resection of lung lesion(s) (preferred), or those who have recently undergone resection of lung lesion(s) will start the Hu5F9-G4 (magrolimab)/dinutuximab within four weeks of resection as outlined in Section 6.4 and Table 6, and
- 2. Those who are scheduled for resection of lung lesions in a stepwise fashion. Patients in this group will initiate treatment between resections as described in Section 6.4. Prior to resection all patients will receive the Hu5F9-G4 (magrolimab)/dinutuximab as outlined in Table 6. If restart of Hu5F9-G4 (magrolimab)/dinutuximab occurs within four (4) weeks of the last dose of Hu5F9-G4 (magrolimab), the patient will pick up the regimen as per the next scheduled regimen cycle for a maximum of 5 cycles postoperatively.
  - If the restart of the Hu5F9-G4 (magrolimab)/dinutuximab is delayed beyond four weeks of the last dose of Hu5F9-G4 (magrolimab), the post-surgical regimen will be conducted as per Table 7 and will require a re-priming dose of Hu59-G4 (magrolimab).

Every attempt will be made to enroll to the "step-wise resection" subgroup prior to the first resection in order to obtain tissue from the resection for research correlatives. If subjects are enrolled after the initial resection, a request will be made

\*\* Cycles may be repeated as long as the patient does not have unacceptable toxicity (see Section 6.3 or Section Error! Reference source not found.) or disease progression to a maximum of 12 cycles

^ Hydroxyzine (0.5-1 mg/kg, Max dose 50 mg) PO may substitute for diphenhydramine

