### 6.2.1.3 Clinical Care for Administration of Hu5F9-G4 (magrolimab)

A priming dose of Hu5F9-G4 (magrolimab) is required on week 1, prior to starting therapy and upon restart of therapy if > four weeks occurs since the last dose of Hu5F9-G4 (magrolimab). The priming dose (1 mg/kg) will be infused over 3 hours (+/- 30 minutes) via a peripheral or central line. Protecting IV bag from light is not required. In-line IV filter set is not required. Subsequent IV doses can be infused over 2 hours (+/- 10 minutes). If Hu5F9-G4 (magrolimab) dosing is ever delayed for greater than 4 weeks, a re-priming dose must be administered on week one, with scheduled dosing restarted 1 week later as depicted in **Figure 2**.

\*\* Patients who are scheduled for resection of lung lesion(s) unilateral or those who have recently undergone resection of lung lesion may continue the regimen for up to 5 cycles post resection in the absence of unacceptable toxicity or disease progression/recurrence.

^ Hydroxyzine (0.5-1 mg/kg, Max dose 50 mg) PO may substitute for diphenhydramine

Hu5F9-G4 (magrolimab) dose will be calculated using the actual body weight of the patient at enrollment (screening visit), and the dose may remain constant throughout the study unless a greater than 10% change in weight is observed.

Hu5F9-G4 (magrolimab) may interfere with the assessment of RBC phenotyping. Hu5F9-G4 (magrolimab) binds to CD47 on RBCs and can mask detection of antibodies to minor antigens to the patient's RBC and ABO/Rh phenotype, DAT and Ab screen. Refer to section 7.2.4 for assessments to be performed and resulted prior to the administration of the priming dose.

Anemia is a known and well described risk for Hu5F9-G4, which can occur in early doses and is transient.

- Within 24 hours prior to the Priming dose (Week 1) of Hu5F9-G4 (magnolimab) infusion, all patients must have a documented hemoglobin level of  $\geq$  9.5 g/dL, per eligibility criterion 3.1.7.
- Within 24 hours prior to the first full dose (Week 2) of Hu5F9-G4 (magnolimab) infusion, all patients must have a documented hemoglobin level of  $\geq 9.0$  g/dL.
- Patients who do not meet these criteria must be transfused and have their hemoglobin rechecked to meet the minimum hemoglobin threshold, as noted above, prior to administrating each of the first 2 doses of Hu5F9-G4 (magrolimab).

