### **6.4** Dose Expansion Cohorts

Upon determining RP2D, enrollment to 4 expansion cohorts will proceed to evaluate evidence of clinical activity (cohorts B1-3) and safety/feasibility of using this combination drug approach after surgery (cohort B4) (Figure 2).

Cohort B1 – Confirmed neuroblastoma: measurable neuroblastoma/ganglioneuroblastoma

Cohort B2 – Evaluable neuroblastoma

Cohort B3 – Measurable osteosarcoma

Cohort B4 – Resectable, pulmonary only relapsed osteosarcoma

All subjects will receive the priming dose of 1 mg/kg Hu5F9-G4 (magrolimab) on Day 1 of week 1. On Day 1 of week 2, subjects will receive Hu5F9-G4 (magrolimab) at RP2D followed by 17.5 mg/m² dinutuximab IV on Days 2-5. Then, they will receive Hu5F9-G4 (magrolimab) at RP2D on Day 1 of week 3 and week 4 (**Figure 2** and **Section 6.2.1.2**).

Cycle 2 will consist of Hu5F9-G4 (magrolimab) at RP2D on Day 1 of week 1 in combination with 17.5 mg/m² dinutuximab IV given on Days 2-5, followed by Hu5F9-G4 (magrolimab) at RP2D on Day 1 of weeks 2-3 (see **Figure 2** and **Section 6.2.1.2**). A disease evaluation will be conducted after Cycle 2 and Cycle 4, and then after every 4 cycles (every 12 weeks) until progressive disease or a maximum of 12 cycles (except cohort four which will have a maximum of five cycles after the patient is rendered No Evidence of Disease (NED)). After Cycle 2, each subsequent cycle will consist of Hu5F9-G4

(magrolimab) administered on Day 1 of weeks 1 and 3 of the cycle (week 2 will be a week of rest), with dinutuximab administration on Day 2-5 of week 1.

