Doses of Hu5F9-G4 (magrolimab) and dinutuximab in the expansion cohorts may be interrupted, delayed or discontinued depending on how well the participant tolerates the treatment. Dosing visits are not skipped, only delayed. Both Hu5F9-G4 (magrolimab) and dinutuximab must be delayed at the same time. Protocol therapy must be discontinued for dose delays greater than 14 days except for reasons outlined in **Section 6.6**. In such cases, the Protocol Principal Investigator must be consulted prior to resuming treatment.

For the expansion cohorts, patients will continue to be monitored for occurrence of DLT during Cycle 1. If 2 of the first 5 patients or if  $\geq$ 2 of 6 patients experience DLT, the Principal Investigator will discuss with all study investigators and with CTEP whether further addition of patients is needed to re-assess the RP2D.

Monitoring of all safety and toxicity data is done by the Principal Investigator and the Corresponding Organization on a real-time basis as data are entered into Medidata Rave using the Web Reporting Module. All participating sites are expected to notify the Principal Investigator when a DLT has occurred.

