## 6.6 **Duration of Follow-Up**

Patients who complete the maximum number of cycles or who met off-therapy criteria other than disease progression will be asked to participate in study follow-up and be evaluated at month 2 ( $\pm$  1 week), month 4 ( $\pm$  2 weeks), month 6 ( $\pm$  4 weeks), month 9 ( $\pm$  4 weeks), and month 12 ( $\pm$  2 months) and then yearly until year 5, or until disease progression.

Follow-up visits will be completed in-person unless the patient does not agree to continue in-person visits. In this case, telephone contact may be arranged to ensure the collection of as many safety and efficacy parameters as possible. The approach taken should be recorded in the CRF. A patient that agrees to modified follow-up is not considered to have withdrawn consent or to have withdrawn from the study.

Patients who develop disease progression during combination therapy will be followed for a minimum of 30 days after the last dose of study drug or study procedure, or until death, whichever occurs first. Patients removed from study for unacceptable adverse event(s) will be followed until resolution or stabilization of the adverse event and disease progression, whichever occurs later.

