### 7.2.2 Magrolimab Dosing Guidance for Planned Surgical Procedures

Surgical Procedure	Magrolimab Dose Guidance	
Minimally invasive procedure  (Examples: biopsies (excluding lung/liver), skin/subcutaneous lesion removal, cataract/glaucoma/eye surgery, cystoscopy)	Hold magrolimab dose 3 days prior to procedure and restart 3 days after.	
Moderately invasive procedure  (Examples: lung/liver biopsy, hysterectomy, cholecystectomy, hip/knee replacement, minor laparoscopic procedures, stent/angioplasty)	Hold magrolimab dose 5 days prior to procedure and restart 5 days after.	
Highly invasive procedure  (Examples: CNS/spine surgery, major vascular surgery, cardiothoracic surgery, major laparoscopic surgery)	Hold magrolimab dose 7 days prior to procedure and restart 7 days after.	

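### The 14-day limit on dose delays takes its exceptions from a section that lists none, and read literally it bars late restarts that the staged B4 surgery rules allow.

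*Combined protocol and SAP*

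**What the plan says.** Section 6.4, on dosing in the expansion cohorts, states: "Protocol therapy must be discontinued for dose delays greater than 14 days except for reasons outlined in" Section 6.6. It adds that the Protocol Principal Investigator must be consulted in such cases before treatment resumes, so exceptions were intended.

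Section 6.6 covers visit timing, telephone contact and follow-up after progression. Patients who finish or stop treatment without progression "will be asked to participate in study follow-up and be evaluated at month 2" and at later visits. It gives no reason for a dose delay. No other section lists exceptions to the limit, and the removal criteria in Section 6.5.1 do not mention it.

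Other operative text provides for longer gaps:

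- The notes to the trial schedule schema (Figure 2) say that pulmonary metastasectomy "will require delay in starting subsequent cycle".
- Section 6.4 lets staged B4 patients resume with Cycle 2 after the second thoracotomy once the physician judges it safe. It sets no maximum.
- Section 6.2.1.2 lets patients who restart within four weeks of the last magrolimab dose pick up the next scheduled cycle. If the restart "is delayed beyond four weeks of the last dose of Hu5F9-G4 (magrolimab), the post-surgical regimen will be conducted" under Table 7, with re-priming.
- Section 6.2.1.3 says: "If Hu5F9-G4 (magrolimab) dosing is ever delayed for greater than 4 weeks, a re-priming dose must be administered on week one", with scheduled dosing restarting a week later.
- For cardiothoracic surgery, Section 7.2.2 says: "Hold magrolimab dose 7 days prior to procedure and restart 7 days after".
- Section 7.1 sends patients off protocol therapy after a delay of more than two weeks for several tabulated toxicities.

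**The concern.** An exception clause that points to the wrong section leaves a mandatory stopping rule with no usable exceptions. The same protocol plans a surgical interruption for part of cohort B4 and writes a full regimen for restarting late. A site that follows Section 6.4 to the letter and a site that follows Table 7 would treat the same patient differently.

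Cohort B4 exists to assess safety and feasibility around surgery in ten evaluable subjects (Section 9.2.3), and Section 3.1.3.4 aims for five of the ten to be staged. If removal or restart depends on which section a site reads, post-operative exposure to the combination will differ between sites for reasons unrelated to the treatment.

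**Working it through.** No stated statistical figure is involved, so the check is day arithmetic on the protocol's own schedule.

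**Inputs**
- Priming is on day 1. In Cycle 1, Section 6.4 gives magrolimab on Day 1 of week 2 and then: "Then, they will receive Hu5F9-G4 (magrolimab) at RP2D on Day 1 of week 3 and week 4". The last Cycle 1 dose is therefore on day 1 + 3 × 7 = 22.
- Cycle 2 for staged B4 patients is due on Day 1 of week 5 (Section 6.4): day 1 + 4 × 7 = 29.
- The limit on delay is 14 days (Section 6.4). The re-priming threshold is 28 days from the last dose (Section 6.2.1.2).
- The plan does not define how a delay is counted. I take delay = restart day − scheduled day.

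**Staged B4 after one cycle**
- The 14-day limit ends on day 29 + 14 = 43, which is 43 − 22 = 21 days after the last dose.
- The four-week branch ends on day 22 + 28 = 50, a delay of 50 − 29 = 21 days.

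| Restart day | Days since last dose | Delay (days) | Section 6.4 limit | B4 restart rules |
|---|---|---|---|---|
| up to 43 | up to 21 | up to 14 | continue | next scheduled cycle |
| 44 to 50 | 22 to 28 | 15 to 21 | discontinue | next scheduled cycle |
| 51 onward | 29 or more | 22 or more | discontinue | Table 7 with re-priming |

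The second and third rows conflict, and the third is the whole of Table 7. The result is the same if more cycles are completed before the second resection: the last magrolimab dose of each later cycle is on Day 1 of week 3, so the next cycle is again due 7 days later.

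**Surgical hold alone**
- Earliest surgery is day 22 + 7 = 29 and earliest restart is day 29 + 7 = 36, a delay of 36 − 29 = 7 days. The hold does not breach the limit. It leaves 43 − 36 = 7 days for a later operation or a longer recovery.

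**How plausible is a longer delay?**
- The plan gives no recovery time after the second thoracotomy. As an assumption, I borrow the intervals it allows between a resection and the first treatment: three weeks (Section 3.1.3.4) or four weeks (Section 6.2.1.2).
- With surgery on day 29, restart would fall on day 29 + 21 = 50 (delay 21 days) or day 29 + 28 = 57 (delay 28 days). Both exceed 14 days, and the second falls under Table 7.

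**Re-priming in the expansion cohorts**
- Read as a delay of more than 28 days, re-priming always lies past 14 days.
- Counted from the last dose, it means a delay of more than 28 − 7 = 21 days on a 7-day interval, or more than 28 − 14 = 14 days on the 14-day interval used from Cycle 3. The nominal schedule again puts every case past the limit.
- The ±2-day visit window opens only a narrow gap on the 14-day interval. If the previous dose was 2 days early, the threshold falls to a delay of 14 − 2 = 12 days, or 12 − 2 = 10 if delay is counted from the end of the window.

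**The case against.** The best defence is that the limit concerns tolerability. Its paragraph opens with interruptions that depend on how well the participant tolerates treatment, and the text just before it gives staged B4 patients their own restart instruction. A site could reasonably let the specific B4 text override the general rule. That reading is available, but it is not written: the discontinuation sentence carries no such restriction, and both the schema and Section 6.2.1.2 describe the surgical gap as a delay. It also leaves a toxicity delay of more than four weeks facing discontinuation in Section 6.4 and re-priming in Section 6.2.1.3.

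A second defence is that Section 6.2.1.3 says how to re-dose, not who may resume, and that it also covers Arm A, whereas the Section 6.4 limit covers only the expansion cohorts. That stands as far as it goes. Within those cohorts, though, the instruction is reached only through an exception that no section supplies.

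A reader might infer more than the documents support:
- **That the hold in Section 7.2.2 itself breaks the limit.** It gives a delay of about 7 days.
- **That the four-week clock runs from surgery.** It runs from the last magrolimab dose.
- **That half of B4 or more is caught.** Five of ten is a best-efforts target, and only staged patients restarting after day 43 are affected.
- **That every patient delayed 15 to 28 days faces contradictory rules.** Outside B4, a delay of 15 to 21 days on a weekly interval is within four weeks of the last dose, so Section 6.2.1.3 does not address it. Only background text in Section 2.1.6 mentions resuming after shorter gaps, and Section 7.1 agrees with a two-week limit for the toxicities it tabulates.
- **That the B4 feasibility decision depends on completion of treatment.** Section 9.2.3 counts complications, with three or more of ten as the threshold.

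**Conclusion.** The point holds as a contradiction between operative rules, caused by a wrong cross-reference. For staged B4 patients after one cycle, restarts on days 44 to 50 and all Table 7 restarts are allowed in one place and barred in another; restarts by day 43 are consistent. Re-priming after a delay of more than four weeks is likewise past the limit in the expansion cohorts.

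The number of patients affected cannot be computed, because the plan gives no distribution of recovery times. It lies between none and all of the staged patients, for whom the target is five of ten. The consequence is uneven post-operative exposure between sites in a ten-patient cohort. Any effect on the complication count is indirect, and no stated design figure changes.

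This rests on counting delay from the scheduled dose day and on reading the Section 6.4 sentence as written. It does not depend on which rule is clinically appropriate.

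**What to change.** - Correct the cross-reference in Section 6.4 and list the permitted exceptions to the 14-day limit in one place.
- State explicitly whether a planned surgical delay, including a Table 7 restart, is an exception.
- Define how a delay is counted: from the scheduled dose day or from the last dose.
- Reconcile Sections 6.2.1.2 (with Tables 6 and 7), 6.2.1.3, 6.4 and the two-week footnotes in Section 7.1 with that list.

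Which limit applies, and to whom, is for the sponsor to decide. The cost is protocol wording in an amendment and a notice to sites; sample size, decision rules and data collection are untouched.

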#### **9.3.3** Sample Size Justification

A minimum of 4 patients will be enrolled on this trial if two patients at Dose Level 1 have DLTs and 2 patients at Dose Level -1 have DLTs.

A maximum of 82 patients will be enrolled on this trial:

- Six patients/dose level at Dose Level 1 and Dose Level -1 = 12
- Three expansion cohorts (B1, B2 and B3) of 20 patients in each cohort
- Ten patients in cohort B4.

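### The Arm B DLT trigger in Section 6.4 has no denominator beyond six patients and does not say whether the count is pooled or per cohort, so it covers only the start of a group of up to 70

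*Combined protocol and SAP*

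**What the plan says.** Section 6.4 states the scope: "For the expansion cohorts, patients will continue to be monitored for occurrence of DLT during Cycle 1". The trigger follows. It opens with "If 2 of the first 5 patients or if" and closes, after a greater-than-or-equal sign, with "2 of 6 patients experience DLT". When it is met, "the Principal Investigator will discuss with all study investigators and with CTEP whether further addition of patients is needed to re-assess the RP2D". No pause in accrual is attached. The same section adds that "All participating sites are expected to notify the Principal Investigator when a DLT has occurred".

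Section 9.3.3 gives the size of Arm B: "Three expansion cohorts (B1, B2 and B3) of 20 patients in each cohort" and "Ten patients in cohort B4".

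Other provisions bear on Arm B safety, but none sets a DLT limit past the sixth patient:
- Section 6.1.1.2 evaluates the first three Arm B patients for DLT, with a 21-day wait before more are treated. These three fall within the first six.
- Section 9.2.2 gives stopping rules for B1 to B3 that count responses only.
- Section 9.2.3 gives a limit for B4 of 3 or more of 10, but it counts complications, not DLTs.
- Sections 6.4, 13.1.1 and 13.1.2 provide real-time review, a DSMC meeting at least every six months and a weekly call that reviews the study chair's DLT evaluations. No DLT count or rate is attached to any of them.

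**The concern.** Safety and tolerability of the combination is the first primary objective (Section 1.1.1). DLTs are assessed in every Arm B patient in Cycle 1, yet the only rule that turns a count into a required review runs out at six. If the first six include no DLT or one, no later DLT rate can set it off.

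Those six may also be a poor guide to the rest of Arm B. Arm A can release the dose after 0 of 3 Cycle 1 DLTs (Section 6.1.1.2). Arm B admits patients up to 35 years, against 18 in Arm A (Section 3.1.5). It starts the combination one week after priming, without the single-agent lead-in (Section 6.2.1.2), and it includes the post-surgical cohort B4. A pooled first six could contain no adult and no B4 patient.

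The wording adds a second problem. The word for first is not repeated before the six, and pooling is not addressed, so sites and CTEP could apply the same sentence differently.

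**Working it through.** **1. Size of Arm B (Section 9.3.3).** Arm A maximum: "Six patients/dose level at Dose Level 1 and Dose Level -1 = 12". Arm B maximum: 3 × 20 + 10 = 70. Total: 12 + 70 = 82, which reproduces the stated maximum. The plan gives no operating characteristic for the DLT trigger, so there is no further figure to reproduce.

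**2. Patients outside the trigger.**
- Pooled, full accrual: 70 − 6 = 64.
- Pooled, B1 to B3 all stopping at 10: 3 × 10 + 10 = 40, and 40 − 6 = 34.
- Per cohort (first six of each of four), full accrual: 70 − 4 × 6 = 46.

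**3. Chance that the pooled trigger fires.** Two DLTs in the first five already imply two in the first six, so the first clause adds nothing to the overall probability. With true DLT rate p,

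P(fire) = 1 − (1 − p)^6 − 6p(1 − p)^5.

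At p = 0.33: 1 − 0.0905 − 0.2673 = 0.642, so it stays silent with probability 0.358. About 0.33 × 64 = 21 DLTs would then be expected among the other 64. The documents give no true or unacceptable DLT rate; every p here is an assumption.

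**4. The same one-third limit read cumulatively.** Flag if DLTs reach 2 of 6, 4 of 12, 6 of 18, 8 of 24 and so on to 22 of 66 (11 looks, pooled). The probability of at least one flag comes from an exact recursion: carry the distribution of the cumulative count forward six patients at a time and remove the flagged paths at each look.

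**5. Per-cohort reading.** P(at least one of four cohorts fires) = 1 − (1 − P(fire))^4. At p = 0.33: 1 − 0.358^4 = 0.98.

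| Assumed DLT rate | Pooled trigger fires | Pooled trigger silent | Cumulative pooled limit flags | Any cohort fires (per-cohort reading) |
|---|---|---|---|---|
| 10% | 11.4% | 88.6% | 12.2% | 38% |
| 20% | 34% | 66% | 42% | 82% |
| 25% | 47% | 53% | 61% | 92% |
| 33% | 64% | 36% | 88% | 98% |
| 40% | 77% | 23% | 98% | 99.7% |

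**6. Repeated flags.** Summing P(count ≥ limit) over the 11 looks gives about 2.2 flagged looks per trial at 25% and about 6 at 33%.

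**7. A rolling reading.** If the six meant any six consecutive patients, simulation gives a trigger in 88% of trials at a 10% rate. That is not workable and is unlikely to be intended.

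**8. Allowing for Arm A.** At p = 0.33, Dose Level 1 passes the Cycle 1 step of Section 6.1.1.2 with probability 0.67³ + 3(0.33)(0.67²)(0.67³) = 0.301 + 0.134 = 0.434. Passing it and then staying silent in Arm B: 0.434 × 0.358 = 0.16, before counting the lead-in or the lower dose level.

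**The case against.** The strongest objection is that the size of the gap depends on a reading the text does not settle. The sentence opens with the expansion cohorts in the plural and does not repeat first before six. If the count is per cohort, 24 patients are covered, and at a 33% rate some cohort fires in 98% of trials. Replacing that with a pooled cumulative rule at 88% would lower detection. This stands, and it shapes the fix.

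Three further points stand in part:
- 64 is a ceiling. Each of B1 to B3 stops at 10 with no responses, which Section 9.2.2 puts at 60% probability when the response rate is 5%.
- The 36% is conditional on Arm B having opened. A reader might infer that over a third of all trials with a 33% DLT rate would go unflagged. The documents do not support that, because Arm A and the check on the first three Arm B patients come first (about 16% on the Cycle 1 step alone).
- One third is not the only defensible boundary, and repeated looks raise the flag rate at 25% from 47% to 61%.

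A reader might also infer that safety oversight ends at patient six, or that the DSMC has no limit at all. Neither follows. DLT notification, real-time review, the weekly call and expedited reporting continue, and nothing prevents the same discussion being held later. Section 13.1.1 only summarises a network monitoring policy that is not included here. What can be said is that this document states no numerical DLT limit for those bodies.

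**Conclusion.** The point holds as a gap in a numerical rule, not as an absence of monitoring. Every workable reading leaves a large part of a fully accrued Arm B beyond the trigger: up to 64 of 70 pooled, or up to 46 of 70 per cohort. The consequence of a missed trigger is that a required discussion does not take place; the trigger never was a stopping rule.

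The detection figures rest on four assumptions: a pooled count, Arm B having opened, independent patients with a constant DLT rate, and accrual to at least 66 for the cumulative limit. The gain is material at rates of 33% and above and almost costless at 10%. At 20 to 25% the extra flags are a real cost, and whether they are wanted depends on which rate the sponsor regards as unacceptable. The plan does not say. DLT is defined for Cycle 1 (Section 6.3), so later toxicity is outside this point. The change should be made, because the rule serves the first primary objective and the data are already collected.

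**What to change.** In Section 6.4:
1. State that the count is pooled over Arm B and that the six are the first six enrolled.
2. Carry the existing one-third review limit forward cumulatively, for example at every further six patients: 4 of 12, 6 of 18, 8 of 24 and so on. Keep the present consequence, a discussion among the Principal Investigator, the investigators and CTEP.
3. If a per-cohort count is intended, keep it and add the cumulative pooled check alongside, so that detection is not lowered.
4. The sponsor may choose a different boundary. Whichever is used, give its operating characteristics over a range of DLT rates and name the rate considered unacceptable.

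The cost is more review discussions when the true rate is about 20 to 25% (34% to 42% and 47% to 61% of trials with at least one flag), some of them repeated at successive looks. No new data, patients or assessments are needed, since each Cycle 1 DLT is already recorded and notified.
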